6.3.1.2.1. Main Analyses

- Estimands:
 - GMTs (Section 2.1).
 - GMFRs (Section 2.1).
 - Percentages of participants with seroresponse
- Analysis sets: Evaluable immunogenicity population, all-available immunogenicity population as applicable (Section 4).
- Analysis time points:
 - GMT: At baseline (before Dose 1), 1 month after Dose 2, 1 month after Dose 3, at Dose 4, 1 month and 6 months after Dose 4.
 - GMFRs: From before vaccination to 1 month after Dose 2, from before vaccination to 1 month after Dose 3, from Dose 4 to 1 month after Dose 4, and from Dose 4 to 6 months after Dose 4.
 - Percentages of participants with seroresponse: 1 Month after Dose 2, 1 month after Dose 3, at Dose 4, and 1 month and 6 months after Dose 4.
- Analysis methodology: GMTs and the associated 2-sided CIs will be derived as described in Section 5.2.2.1. GMFRs and the associated 2-sided CIs will be calculated as described in Section 5.2.2.2. Percentages of participants with seroresponse and the associated 2-sided Clopper-Pearson CIs will be derived as described in Section 5.2.1. Seroresponse is defined as achieving a ≥4-fold rise from baseline (before Dose 1). If the baseline

PFIZER GENERAL BUSINESS

measurement is below the LLOQ, the postvaccination measure of \geq 4 × LLOQ is considered seroresponse.

- Intercurrent events and missing data: Serology data deemed unevaluable because of noncompliance with the key protocol criteria will be excluded. Missing data will not be imputed.
- Reporting results: GMTs, GMFRs, counts and percentages of participants with seroresponse, and the associated 2-sided 95% CIs will be provided for each disease subset in participants ≥18 years of age and for each disease subset in each of the younger age groups (≥2 to <5, ≥5 to <12, and ≥12 to <18 years of age) at each analysis time point.

Figures:

Empirical RCDCs will be provided for SARS-CoV-2 neutralizing titers at each analysis time point for each age group and disease subset (Section 5.2.2.3).

6.3.2. Efficacy Endpoints

6.3.2.1. COVID-19 Incidence per 1000 Person-Years of Follow-up Based on Central Laboratory or Locally Confirmed NAAT

6.3.2.1.1. Main Analyses

- Estimand:
 - COVID-19 incidence per 1000 person-years of follow-up (Section 2.1).
- Analysis set: Safety population (Section 4).
- Analysis time point: End of the surveillance period.
- Analysis methodology: Incidence rate (per 1000 person-years of follow-up) and the exact
 2-sided 95% CI based on Poisson distribution (Section 5.2.3) for confirmed COVID-19 cases. Kaplan-Meier cumulative incidence of COVID-19 cases over time will be plotted.
- Intercurrent events and missing data: Missing data will not be imputed.
- Reporting results: Counts, incidence of confirmed COVID-19 cases per 1000 person-years of follow-up, the associated 2-sided 95% CIs, and Kaplan-Meier cumulative incidence curves will be provided.

PFIZER GENERAL BUSINESS

6.3.2.2. MIS-C Incidence per 1000 Person-Years of Follow-up

6.3.2.2.1. Main Analyses

- Estimand:
 - MIS-C incidence per 1000 person-years of follow-up (Section 2.1).
- Analysis set: Safety population (Section 4).
- Analysis time point: End of the surveillance period.
- Analysis methodology: Incidence rate (per 1000 person-years of follow-up) and the exact 2-sided 95% CI based on Poisson distribution (Section 5.2.3) for confirmed MIS-C cases. Kaplan-Meier cumulative incidence of MIS-C cases over time will be plotted.
- Intercurrent events and missing data: Missing data will not be imputed.
- Reporting results: Counts, incidence of confirmed MIS-C per 1000 person-years of follow-up, the associated 2-sided 95% CIs, and Kaplan-Meier cumulative incidence curves will be provided.

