- This telephone contact will be recorded in the participant's source documentation and the CRF.

If the participant is unable to attend the unscheduled visit, or the PI or authorized designee determined it was not needed, any ongoing local reactions/systemic events must be assessed at the next study visit.

During the unscheduled visit, the reactions/events should be assessed by the investigator or a medically qualified member of the study staff such as a study physician or a study nurse, as applicable to the investigator's local practice, who will:

- Measure body temperature (°F/°C).
- Measure minimum and maximum diameters of redness (if present).
- Measure minimum and maximum diameters of swelling (if present).
- Assess injection site pain (if present) in accordance with the grades provided in Section 8.2.4.2.
- Assess systemic events (if present) in accordance with the grades provided in Section 8.2.4.3.
- Assess for other findings associated with the reaction/event and record on the AE page of the CRF, if appropriate.
- The investigator or an authorized designee will complete the unscheduled visit assessment page of the CRF.

8.11. COVID-19 Surveillance (All Participants) and MIS-C Surveillance (Participants <21 Years of Age)

COVID-19 Surveillance: If a participant experiences any 1 of the following within a 24-hour period, from Visit 1 onwards (irrespective of perceived etiology or clinical significance), the participant or his/her parent(s)/legal guardian is instructed to contact the site immediately and, if in the opinion of the investigator a COVID-19/MIS-C illness visit is indicated, a potential COVID-19/MIS-C illness visit should be conducted. The test and visit would be optimal within 3 days after symptom onset (and at the latest 4 days after symptom resolution). During the 7 days following each vaccination, potential COVID-19 symptoms that overlap with specific systemic events (ie, fever, chills, new or increased muscle pain, diarrhea, vomiting) should not trigger a potential COVID-19 illness visit unless, in the investigator's opinion, the clinical picture is more indicative of a possible COVID-19 illness than vaccine reactogenicity.

Note that:

- If new symptoms are reported within 4 days after resolution of all previous symptoms, they will be considered as part of a single illness and a second illness visit is not required;

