- Surveillance of potential COVID-19 symptoms should continue even if a participant has a positive SARS-CoV-2 test earlier in the study.

If, in the investigator's opinion, the symptoms are considered more likely to be vaccine reactogenicity, but a participant is required to demonstrate that he or she is SARS-CoV-2—negative, a local SARS-CoV-2 test may be performed. If the result is positive, the symptoms should be recorded as a potential COVID-19 illness; if not, the symptoms should be recorded as AEs (unless already captured in the reactogenicity e-diary).

MIS-C Surveillance: If a participant experiences a hospitalization for a severe illness with no other alternative etiology, the participant's parent(s)/legal guardian is instructed to contact the site immediately and participate in an in-person or telehealth visit as soon as possible, optimally within 3 days after symptom onset (and at the latest 4 days after symptom resolution). Note that if new symptoms are reported within 4 days after resolution of all previous symptoms, they will be considered as part of a single illness, and a second illness visit is not required.

COVID-19/MIS-C Surveillance

The participant or participant's parent(s)/legal guardian may utilize a COVID-19/MIS-C illness e-diary through an app (see Section 8.2.4) installed on a provisioned device or on a personal device to report any symptoms listed below. Note that this does not substitute for a participant's routine medical care. Therefore, participants should be encouraged to seek care, if appropriate, from their usual provider.

- A diagnosis of COVID-19;
- Fever;
- New or increased cough;
- New or increased shortness of breath;
- Chills;
- New or increased muscle pain;
- New loss of taste/smell;
- Sore throat:
- Diarrhea;
- Vomiting.

In addition, the following symptoms are for participants who are ≤ 12 years of age:

- Hospitalization for a severe illness with no other alternative etiology;
- Hospitalization due to confirmed COVID-19 infection;
- Inability to eat/poor feeding in participants <5 years of age;
- Abdominal pain.

Note that:

- If new symptoms are reported within 4 days after resolution of all previous symptoms, they will be considered as part of a single illness, and a second illness visit is not required.
- Surveillance of potential COVID-19 symptoms should continue even if a participant has a positive SARS-CoV-2 test earlier in the study.

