2.2. Study Design

This is a Phase 2b, open-label study with BNT162b2 in immunocompromised participants ≥18 years of age treated for NSCLC or CLL, receiving hemodialysis treatment secondary to

PFIZER GENERAL BUSINESS

groups:

end-stage renal disease, or receiving immunomodulator therapy for an autoimmune inflammatory disorder, and in immunocompromised participants ≥2 to <18 years of age receiving immunomodulator therapy or who have undergone solid organ transplant (within the previous 3 months) and are on immunosuppression or who have undergone bone marrow or stem cell transplant at least 6 months prior to enrollment. This study will evaluate the safety, tolerability, and immunogenicity of BNT162b2:

• Open-label; 4 doses, with the primary series consisting of 2 doses separated by 21 days and a third dose occurring 28 days after Dose 2. The fourth (booster) dose will occur 3 to 6 months after Dose 3. Note that the timing of the fourth dose should be determined by the investigator's discretion, considering such factors as the participant's underlying condition and level of immunosuppression, the evolving clinical literature, the COVID-19 incidence in the participant's geographic area, and the potential for increased reactogenicity with Dose 4 occurring earlier. Additionally, although more data are needed for COVID-19 vaccines, there is a risk of reduced immunogenicity and antibody persistence with a shorter interval between Dose 3 and Dose 4. Investigators are encouraged to weigh the risks and benefits for each participant and make an individualized decision on the timing of the fourth dose, provided it falls within the minimum and maximum time frames detailed above. Depending on the timing of Dose 4, participants are expected to participate for up to 14 months, with a maximum of approximately 15 months.

The dose for each of the 4 vaccinations will depend upon the age of the participant at the time of vaccination, as follows:

- For participants who are ≥12 years of age (on the day of vaccination): at a 30-µg dose level
- For participants who are ≥5 to <12 years of age (on the day of vaccination): at a 10-μg dose level
- For participants who are <5 years of age (on the day of vaccination): at a 3-µg dose level Approximately 124 participants in total have been enrolled, with the following breakdown:
- In approximately 7 participants who are ≥18 years of age (at Visit 1) in the following

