4. ANALYSIS SETS (POPULATIONS FOR ANALYSIS)

Analysis populations are defined for the statistical analysis of safety, immunogenicity, and efficacy results in the table below. For the specified criteria in each population definition, data for all participants will be assessed to determine if participants meet the criteria for inclusion in each analysis population prior to releasing the database, and the classifications will be documented per standard operating procedures.

PFIZER GENERAL BUSINESS

Population	Description		
Enrolled	All participants who have a signed ICD and assent (where appropriate).		
Assigned to study intervention	All participants who are assigned a randomization number in the IRT system.		
Dose 3 evaluable immunogenicity	 All participants who Are eligible; Receive 3 doses of the vaccine to which they are assigned, with Dose 2 received within 19 to 42 days after Dose 1 and Dose 3 received within 28 to 189 days, inclusive, after Dose 2; Have at least 1 valid and determinate immunogenicity result within an appropriate window at Visit 7 (28-42 days, inclusive, after Dose 3); and Have no other important protocol deviations as determined by the clinician. 		
Dose 4 evaluable immunogenicity	 All participants who Are eligible; Receive 4 doses of the vaccine to which they are assigned, with Dose 2 received within the predefined window (19-42 days, inclusive, after Dose 1), Dose 3 received within 28 to 189 days, inclusive, after Dose 2, and Dose 4 received within the predefined window (91-189 days, inclusive, after Dose 3); Have at least 1 valid and determinate immunogenicity result within an appropriate window at Visit 9 (28-42 days, inclusive, after Dose 4); and Have no other important protocol deviations as determined by the clinician. 		
All-available immunogenicity	All participants who receive at least 1 dose of the study intervention with at least 1 valid and determinate immunogenicity result after vaccination.		
Safety	All participants who receive at least 1 dose of the study intervention.		

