5.2.3. Analyses for Count Data

Descriptive statistics for count data are incidence rate, the numerator (number of events observed), and the denominator (total person-years of follow-up) used in the incidence rate calculation, and the 95% CIs where applicable.

PFIZER GENERAL BUSINESS

The exact 95% CI for incidence rates for each group will be computed using the method of Ulm² based on the link between the chi-square distribution and the Poisson distribution.

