 - <70 + (age in years × 2) for age up to 10 years, <90 for age ≥10 years; or requiring vasoactive drugs to maintain BP in the normal range;
- Significant acute renal failure: serum creatinine ≥2 times the ULN for age or a 2-fold increase in baseline creatinine:
- Significant GI/hepatic failure: TBili ≥4 mg/dL or ALT 2 times the ULN for age;

PFIZER GENERAL BUSINESS

- Significant neurological dysfunction: Glasgow Coma Scale score ≤11 or an acute change in mental status with a decrease in Glasgow Coma Scale score ≥3 points from abnormal baseline⁶;
- Admission to an ICU;
- Death.

Table 8. RR and HR, by Age, Indicative of Severe Systemic Illness

Participant Age	RR	HR
2 to <3 Years	>38	>142
3 to <4 Years	>33	>136
4 to <6 Years	>29	>131
6 to <8 Years	>27	>123
8 to <12 Years	>25	>115

Abbreviations: HR = heart rate; RR = respiratory rate.

Source: Fleming S, Thompson M, Stevens R, et al. Normal ranges of heart rate and respiratory rate in children from birth to 18 years of age: a systematic review of observational studies. Lancet 2011;377(9770):1011-8.

Confirmed MIS-C definition⁷: as per the CDC MIS-C case definition:

- An individual <21 years of age presenting with fever (≥38.0°C for ≥24 hours or report of subjective fever lasting ≥24 hours); AND
- Laboratory evidence of inflammation (based on local laboratory ranges) including, but not limited to, 1 or more of the following: an elevated CRP, ESR, fibrinogen, procalcitonin, D-dimer, ferritin, LDH, or IL-6, elevated neutrophils, reduced lymphocytes, and low albumin; AND
- Evidence of clinically severe illness requiring hospitalization (definition as noted above for severe disease), with multisystem (≥2) organ involvement:
 - Cardiac (eg, shock, elevated troponin, elevated BNP, abnormal echocardiogram, arrhythmia);
 - Renal (eg, acute kidney injury);
 - o Respiratory (eg, pneumonia, ARDS, pulmonary embolism);
 - o Hematologic (eg, elevated D-dimers, thrombophilia, or thrombocytopenia);

PFIZER GENERAL BUSINESS

- o GI/hepatic (eg, elevated bilirubin, elevated liver enzymes, or diarrhea);
- o Dermatologic (eg, rash, mucocutaneous lesions);
- o Neurological (eg, CVA, aseptic meningitis, encephalopathy); AND
- No alternative plausible diagnoses; AND
- Positive for current or recent SARS-CoV-2 infection by RT-PCR, serology, or antigen test; OR
- COVID-19 exposure within the 4 weeks prior to the onset of symptoms.

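### SAP 6.3.2.2.1 computes MIS-C incidence in the all-age safety population, although only participants under 21 can be a case; the rate is understated by at most a factor of about 1.06

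*SAP*

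**What the plan says.** - **Case definition.** SAP Appendix 2 opens the confirmed MIS-C definition with "An individual <21 years of age presenting with fever". Protocol 8.1.2 has the same age limit.
- **Analysis set.** SAP 6.3.2.2.1 gives "Analysis set: Safety population (Section 4" for this endpoint. SAP Section 4 defines that population as "All participants who receive at least 1 dose of the study intervention", with no age limit.
- **Rate and interval.** SAP 5.2.3 uses "the denominator (total person-years of follow-up) used in the incidence rate calculation". SAP 6.3.2.2.1 adds an exact "2-sided 95% CI based on Poisson distribution (Section 5.2.3) for confirmed MIS-C cases" and a Kaplan-Meier curve. Protocol 9.3.4 also asks for counts and a rate per 1000 person-years, and names no age limit.
- **Surveillance.** The heading of Protocol 8.11 reads "MIS-C Surveillance (Participants <21 Years of Age". Its MIS-C paragraph is triggered by "hospitalization for a severe illness with no other alternative etiology" and sets no limit at age 12. Further down the same section, a list of items that may be reported in the illness e-diary places that trigger under an addition for participants aged 12 or younger.

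**The concern.** An incidence rate should count only person-time during which the event can occur. By the trial's own definition a participant aged 21 or older cannot have MIS-C, yet the SAP includes that person's follow-up in the denominator and keeps the person in the Kaplan-Meier risk set. The MIS-C section closely follows the COVID-19 section (SAP 6.3.2.1.1), where an all-age set is right because the COVID-19 definition applies to all participants. The age limit of MIS-C was not carried over.

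Any resulting error understates the rate. With about 124 participants, zero MIS-C cases is a plausible result, and the upper confidence limit would then be the main information reported. Protocol 2.3 designates the study as a post-authorization safety study with regulatory commitments, and Protocol 2.3.1 lists MIS-C in the risk assessment.

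**Working it through.** **Inputs.** SAP 2.2 states "Approximately 124 participants in total have been enrolled, with the following breakdown".

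- Adults (18 or older at Visit 1): 1 NSCLC + 0 CLL + 1 hemodialysis + 5 autoimmune = 7.
- Under 18 at Visit 1: 37 + 65 + 15 = 117.
- Total: 7 + 117 = 124, which reproduces the plan's figure.
- Follow-up: up to 14 months, with a maximum of about 15 (SAP 2.2). The documents give no expected person-years and no expected MIS-C count. I assume equal follow-up for everyone and show 10 to 15 months.
- Adults aged 21 or older: not given. I assume a range of 0 to 7.

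Nobody under 18 at Visit 1 can reach 21 within about 15 months, so all 117 stay at risk throughout. Only the 7 adults can contribute person-time not at risk.

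**Relative size.** If k participants are 21 or older, the SAP denominator is too large by a factor of 124/(124 − k).

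- k = 0: factor 1.00, no effect.
- k = 7: 7/124 = 5.6% of person-time is not at risk, and the factor is 124/117 = 1.060.

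**Upper limit with 0 cases.** The exact 2-sided 95% Poisson upper limit is −ln(0.025) = 3.689 events, divided by person-years (PY). The ceiling k = 7 gives:

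| Assumed months each | PY, 124 people | PY, 117 people | Upper limit per 1000 PY, SAP set | Upper limit per 1000 PY, under 21 |
|---|---|---|---|---|
| 10 | 103.3 | 97.5 | 35.7 | 37.8 |
| 14 | 144.7 | 136.5 | 25.5 | 27.0 |
| 15 | 155.0 | 146.25 | 23.8 | 25.2 |

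For example, at 14 months: 124 × 14/12 = 144.7 and 3.689/144.7 × 1000 = 25.5; 117 × 14/12 = 136.5 and 3.689/136.5 × 1000 = 27.0.

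**With 1 case at 14 months.** The SAP set gives 1/144.7 × 1000 = 6.9 (95% CI 0.2 to 38.5). The under-21 set gives 1/136.5 × 1000 = 7.3 (0.2 to 40.8). The shift is small beside the width of the interval.

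**Does other SAP text repair this?**

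- SAP 5.2 requires separate analysis by age and disease group for safety and immunogenicity data. SAP 3.3.2 and 6.3.2 class MIS-C incidence as an efficacy endpoint.
- The AE and SAE sections (SAP 6.1.2.3.1 and 6.1.2.4.1) each state reporting by age group. SAP 6.3.2.2.1 does not.
- SAP 6.4 plans no subgroup analysis.

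As written, no MIS-C rate is clearly specified for the people who can have MIS-C.

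**The case against.** **The effect may be nil.** Adults aged 18 to 20 can be cases, and the number aged 21 or older is not stated. With 0 cases the point estimate and the Kaplan-Meier curve are the same either way; only the upper limit moves. The endpoint is exploratory and descriptive. All of this stands and is why the point is minor.

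**The person-years are illustrative.** Participation is up to 14 months, not 14 months each, and SAP Appendix 2 ends surveillance for all efficacy endpoints at the first COVID-19 case or the end of study. This stands too. The ratio is more useful than the absolute figures, and it rests on equal follow-up.

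**Reporting by group may already solve it.** SAP 5.2.3 describes exact intervals for incidence rates in each group. If the groups are the age and disease groups of SAP 5.2, the under-18 rates already have clean denominators. That reading is possible, but SAP 6.3.2.2.1 does not state it, so the text is unclear at best.

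**A stronger reading that does not hold.** From the age-12 limit in the Protocol 8.11 list, a reader might infer that cases at 13 to 20 years would be missed, or that numerator and denominator cover different people. The documents do not support either:

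- The list does not define a case. Confirmed MIS-C counts at any age under 21, and everyone who can be a case is in the safety population if dosed. The at-risk group is a subset of the denominator, at least 117 of 124.
- The list concerns items in an e-diary whose use is optional. At most about 15 adolescents (fewer, since 12-year-olds are included), plus any adults aged 18 to 20, lose those items.
- Other routes still reach them: the MIS-C paragraph of 8.11, footnote a of the Schedule of Activities, the instruction at Visits 1 to 9 to report any hospitalization at once, and SAE collection through the end of study, with inpatient hospitalization as a criterion (Protocol 8.3.1 and 10.2.2). Fever, which the MIS-C definition requires, is on the all-age list.

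**Conclusion.** The denominator point holds. SAP 6.3.2.2.1 lets in person-time from people who cannot be a case, and no other text clearly corrects it. If any participants are 21 or older, the rate and its upper limit are too low; the error cannot go the other way. The understatement is at most a factor of 1.06, reached only if all 7 adults are 21 or older and follow-up is equal across ages, and it is nil if none are. This is a low-priority correction that does not threaten any conclusion of the study.

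The age limits within Protocol 8.11 (under 21 in the heading, no age-12 limit in the MIS-C paragraph, 12 or younger in the e-diary list) conflict and must be reconciled. That is a wording point. Lost cases are not shown.

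**What to change.** **SAP 6.3.2.2.1.** Change the analysis set to safety-population participants under 21 years of age, count person-time only until the 21st birthday, and use the same set for the Kaplan-Meier curve.

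The cost is a short SAP edit. Full date of birth is already collected (Protocol Section 8), so no new data are needed. The endpoint is exploratory, so the rule in SAP Section 5 that major changes to primary endpoints also need a protocol amendment does not apply. The one downside is a slightly less favourable upper limit.

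**Protocol 8.11.** Reconcile the e-diary list with the section heading and the MIS-C paragraph. This costs more than the SAP edit: it would be a protocol amendment needing ethics approval (Protocol 10.1.1), and possibly an e-diary change, in a study whose enrollment is described as already done. If an amendment is no longer practical, the study report can state which ages were offered the hospitalization items in the e-diary.
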